4.3.6 Reporting of suspected unexpected serious adverse reactions by Investigator	
	15
5 INVESTIGATIONAL MEDICINAL PRODUCT	15
5.1 INVESTIGATIONAL MEDICINAL PRODUCT AND COMPARATOR	15
5.2 SUPPLY, PACKAGING, LABELLING, HANDLING AND STORAGE	16
5.3 DOSAGE AND ADMINISTRATION	16
5.4 DURATION OF TREATMENT	17
5.5 METHODS FOR ASSIGNING SUBJECTS TO TREATMENT	17
5.6 CONCOMITANT MEDICATION	17
5.7 IMP ACCOUNTABILITY	17
6 VARIABLES	17
7 STATISTICAL METHODOLOGY AND DATA MANAGEMENT	18
7.1 STATISTICAL ANALYSIS PLAN	18
7.2 STUDY POPULATIONS	18
7.3 DESCRIPTIVE STATISTICS	18
7.4 MISSING DATA	18
7.5 DATA COLLECTION / CASE REPORT FORMS	18
7.6 DATA MANAGEMENT	18
8 REGULATORY AND ADMINISTRATIVE PROCEDURES	19
8.1 INSTITUTIONAL REVIEW	19
8.2 PATIENT INFORMATION / INFORMED CONSENT	19
8.3 SUBJECT CONFIDENTIALITY	19

8.4	SUBJECT TREATMENT PLAN	19
8.5	GCP	19
8.6	RECORD RETENTION.....	19
8.7	QUALITY ASSURANCE.....	20
8.8	INSURANCE AND LIABILITY	20
8.9	END OF TRIAL	20
8.10	STUDY REPORT	20
8.11	PUBLICATION AND DATA RIGHTS	20
9	REFERENCES	21
10	SIGNATURES	22
11	SIGNATURE PAGE FOR INVESTIGATORS	23
12	APPENDICES	24
12.1	PATIENT INFORMATION SHEET /INFORMED CONSENT FORM	24
12.2	QUESTIONNAIRES.....	24

PROTOCOL OUTLINE

Working title		Implementation of pre-exposure prophylaxis (PrEP) in subjects at particular high risk for human immunodeficiency virus (HIV) acquisition - an evaluation study.
Study objectives		
Assess the impact of PrEP on the sexual and psychological health of PrEP usersIncidence of sexually transmitted infections (STIs) in PrEP users compared to those not taking PrEPAssessment of drug complianceIncidence of HIV seroconversion despite PrEPFrequency and development of drug resistance in subjects who HIV-seroconvert (if any)
Selection criteria (abbreviated)	Inclusion	
Male, female or transgender persons aged \geq 18 years who are offered or have started PrEP in routine clinical practice, and 2, 3, 4, 5, 6 or 7 (below).Men who have sex with men (MSM) and transgender persons;
who have had unprotected anal sex with two or more partners during the last six months and/orwho have had bacterial sexually transmittable infection(s) during the last twelve months and/orwho have used post-exposure prophylaxis(PEP) during the last twelve months and/orwho use recreational drugs when having sexIndication for PrEP is present according to the assessment of the health care providerMen and women who are at high risk of HIV according to their sexual practicesHIV-negative partner of a HIV-positive person not yet virologically suppressed by antiretroviral therapy (ART)Sex workers with inconsistent condom usePersons with inconsistent condom use with sexual partners in / from countries with a high prevalence of HIV (COHP)
	Exclusion	
HIV positive subjectsSubjects who cannot take FTC/TDF due to contraindications
	Control group	
Enrolled patients will be regarded as their own control when it comes to their sexual health and quality of life reported for period prior to inclusion in the study.Subjects diagnosed with HIV in general clinical practice and referred to the out-patient clinic at the Dept. of Infectious Diseases, OUS, for details, see 3.3.2.Frequency of STI reported to the National Institute of Public Health (MSIS) will be compared with the frequency of STIs in the study cohort.
Methods & procedures		
PrEP assessment occurs on designated clinic days at The Olafia clinic and will be performed by a team of doctors and nurses specifically trained in PrEP assessment. Persons may be self-referred or referred from other health providers for PrEP assessment. At other sites this will be organized according to the local resources.
 
Subjects will be provided with written and oral information about the study and invited to sign an informed consent form. Subjects not consenting to participation in the study will still be offered PrEP (if indicated) and follow up according to national (NFIM) and local (Olafiaklinikken) guidelines.
 
Subjects who sign the consent form will go through an enrolment procedure to ensure that the PrEP treatment is indicated according to inclusion/exclusion criteria (based on national and local guidelines). Study participants will be asked to complete a questionnaire with detailed information on demographics, medical history, sexual behaviour the last 6 months, perception of HIV risk at the last condomless sex, risk management strategies, personal history of STIs, HIV& STI testing frequency and drug/

		
alcohol use.
 
Subject will be screened for the following STIs during the enrolment visit: HIV, syphilis, hepatitis A/B/C, Chlamydia trachomatis, Neisseria gonorrhoea, and Mycoplasma genitalium.
 
Participants will be asked to return approximately one week later to discuss their HIV result and whether they wish to proceed with initiation of PrEP.
 
The decision regarding initiation of continuous or intermittent PrEP is based on a discussion with the subject and study team (doctor/nurse), subjects' personal preference, medical considerations and whether the expected use will surpass more than 15-20 tablets of FTC/TDF per month.
 
HIV testing will be repeated at 2, 4 and 8 weeks from the most recent high risk exposure (for HIV acquisition) prior to initiation of PrEP. Thereafter participants are requested to visit the clinic every 3 months from PrEP initiation (for the next 24 months) for HIV & STI testing, evaluation of compliance (blood test for drug monitoring in continuous PrEP arm, drug diaries in both continuous and intermittent PrEP arms), assessment of clinical and/or biochemical adverse reactions and quality of life and sexual behaviour assessment. Subjects will be asked to answer the same questions regarding sexual behaviour and quality of life at follow up visits as at inclusion study visit.

Statistics	Sample size	Not applicable
	Methods	Categorical variables will be described by means of absolute and relative frequencies, while continuous variables by means of mean, standard deviation, quartiles, min and max.

LIST OF ABBREVIATIONS

AE	Adverse Event
ART	Anti retroviral therapy
COHP	Country of high prevalence of HIV
CRA	Clinical Research Associate
CRF	Case Report Form
CSR	Clinical Study Report
CT	Chlamydia trachomatis
DM	Data Manager
EC	Ethics Committee
eCRF	Electronic Case Report Form
EDC	Electronic Data Capture
EMA	The European Medicines Agency
GCP	Good Clinical Practice
HIV	Human Immunodeficiency Virus
ICF	Informed Consent Form
ICH	International Conference on Harmonisation
IMP	Investigational Medicinal Product
ISF	Investigator Site File
ITT	Intention-To-Treat
MG	Mycoplasma genitalium
MSM	Men who have sex with men
NG	Neisseria gonorrhoea
PI	Principal Investigator
PIS	Patient Information Sheet
PrEP	Pre-Exposure Prophylaxis
SAE	Serious Adverse Event
SD	Standard Deviation
SDV	Source Data Verification
SUSAR	Suspected Unexpected Serious Adverse Reaction
STI	Sexually Transmitted Infections
TAF	Tenofovir alafenamide
TDF	Tenofovir disoproxil fumarate

1 INTRODUCTION

Pre-exposure prophylaxis (PrEP) is the pre-emptive use of drugs to prevent disease in people who have not yet been exposed to the disease-causing agent. In July 2016 the European Medicine Agency (EMA) recommended that the EU commission should grant a marketing approval for Truvada® (tenofovir disoproxil fumarate + emtricitabine) as PrEP in combination with safer sex practices to reduce the risk of sexually acquired HIV infections. The Committee for Medicinal Products for Human Use (CHMP) based their decision on clinical trials which show substantial reduction in risk for HIV infections when Truvada® was used as PrEP. Truvada® is approved for PrEP in USA since 2012.

The introduction of PrEP is mainly based on two studies, the IPERGAY (Molina JM. Et al., 2015) and PROUD studies (McCormack S et al., 2016). In these two studies Truvada® was given "on demand" or continuously, respectively. The protective effect was comparable in the two studies at 86%. In people who have high risk sex several times per week the risk for HIV acquisition is ongoing and continuous HIV protection is required. On the other hand individuals who have high risk sex on a predictable, yet infrequent basis may not need continuous PrEP. In the latter case intermittent ("on demand") PrEP may be more appropriate.

Intermittent PrEP should reduce cost and the risk of adverse drug reactions as drug exposure is minimized. The Norwegian National Guidelines on HIV management (NFIM) and European guidelines (EACS) recommend both intermittent and continuous PrEP as options based on the frequency of risk behaviour.

Descovy® (tenofovir alafenamide + emtricitabine) is a newer alternative to Truvada® with less risk of renal adverse effects. Many HIV physicians are replacing Truvada® with Descovy® as NRTI backbone. Studies are ongoing to evaluate Descovy® as PrEP.

The incidence of bacterial STIs appears to have increased in some settings where PrEP has been available, whilst others report a decreased incidence of bacterial STIs in PrEP users. It is important to see what implications PrEP will have on the incidence of STIs and sexual behaviour of PrEP users in Norway.

Drug resistance is an important factor in HIV treatment. Usually HIV drug resistance occurs in an individual as a result of poor adherence to ART. Alternatively, HIV drug resistance may be acquired at the time of transmission if infected by a person already harbouring a resistant virus, i.e. transmitted drug resistance. On a worldwide basis, three cases of HIV seroconversions despite good PrEP adherence have been reported [Knox D et al. 2016]. In one case, the PrEP user was infected by a virus resistant to tenofovir + emtricitabine. According to national surveillance data for drug resistance among newly diagnosed patients in Norway, the frequency of tenofovir and/or emtricitabine resistance is low: in 2015, two of the 149 samples tested were resistant to emtricitabine (1%), and none to tenofovir

In existing guidelines in Europe and US, there is a consensus that PrEP should be made available for those at highest risk of HIV infection. This particularly includes men who have sex with men (MSM) and male to female transgender persons, based on the incidence of HIV infection, individual risk behaviour and other factors affecting sexual behaviour.

The World Health Organization (WHO)'s guidelines for PrEP (from 2015) identify populations with a HIV infection incidence of 3 per 100 persons/ year. These include sub-populations of MSM, male to female transgender persons and heterosexuals with a HIV positive partner not virologically suppressed. The risk will vary and will be evaluated in each individual case.

The European AIDS Clinical Society (EACS) guidelines recommend that PrEP should be considered for HIV negative MSM and transgender persons who are inconsistent in their use of condoms when having sex with casual partners or HIV positive partners who are not on treatment. Centre for Disease Control and Prevention (CDC) in US recommend PrEP to MSM with high risk of HIV infection, based on individual risk. As in several other countries, e.g. the United Kingdom, The Netherlands and France, the Norwegian Associations for Infectious

Diseases has settled on a similar definition of risk and recommend PrEP to the similar target populations in its guidelines.

The number of sexually active homosexual, bisexual or other MSM in Norway is unknown. Based on previous national and international population studies, the proportion of MSM in the male population is estimated to be between 3-7%. Although MSM constitute a relatively small proportion of the male population, the group represent more than half of the annual HIV cases. This indicates a substantial risk of HIV among MSM.

In the UN's new political declaration about HIV and AIDS June 2016, MSM were estimated to have 24 times higher risk of HIV infection than other adults in the general population. Similarly, transgender persons were estimated to have 49 times higher risk of HIV than other adults in the general population. PrEP is mentioned in the declaration as one of several biomedical interventions that should be considered to reach the goal to eliminate HIV and AIDS within 2030.

In EU and EEA there has been an increase in new HIV cases among MSM. 53% of all new HIV cases are found among MSM and this group is the only group of the population that show an increase in new HIV cases.

Based on the national HIV surveillance figures, MSM are the obvious target group for PrEP in Norway as MSM constitute by far the largest single group that contract HIV infection. During the period 1986-2016 MSM constituted 32,8% of all HIV cases reported to the National Institute of Public Health (NIPH). In 2016 a total of 220 new HIV diagnosis were registered of whom 70 acquired their HIV infection in their country of origin prior to immigration and thus not eligible for preventive measures. Among the 150 new HIV cases in people residing in Norway and eligible to preventive measures, MSM were over-represented with 87 (58%) new HIV infections. The majority of new infections found in MSM occurred as a result of sex with a casual partners either in Norway or abroad. An increasing proportion of new infections among MSM occurred abroad in 2016 (59%) while new infections among MSM acquired in Norway remained stable.

Despite the significant preventive efforts to reduce HIV infections in the past decades, the incidence in MSM has plateaued at a higher level after the turn of the millennium. In 2015 a reduction in newly diagnosed HIV cases was reported for the first time. Early detection of HIV and treatment as prevention may have played a positive role in reducing HIV transmission, however, numbers increased again in 2016. Over 90% of HIV positive MSM in Norway are treated and virologically suppressed and thereby considered not infectious.

Since the early days of the HIV epidemic, changes in sexual behaviour and increased use of condoms have been advocated and the only tools available to prevent HIV transmission. Later, frequent testing and treatment of STIs (including HIV) have been added to the preventive measures available. Still, this does not seem to be sufficient for all MSM. The use of PrEP is therefore likely an important supplement to prevent HIV infections in MSM at high risk for HIV acquisition.

In 2016 the incidence of HIV dropped by 30-40% among MSM in London. Participation in PROUD and the availability of PrEP (for those who can purchase it privately) has been proposed as the main reason for this substantial drop in the incidence [press release 56 Dean Street].

1.1 Aim of Present Study

The main objective of this study is to monitor the impact of PrEP on the subject's psychological and sexual health. It is also important to monitor the adherence to PrEP, development of drug resistance (in the case of undetected HIV infection at initiation of PrEP), frequency of other STIs, changes in sexual behaviour, recreational drug use and quality of life. PrEP has proven to be effective in reducing the sexual acquisition of HIV, however this requires that the medication is taken as prescribed, whilst the subject is exposed to high risk of infection.

2 OBJECTIVES

This study is designed to evaluate implementation of PrEP treatment as a part of the general HIV preventive program in Norway. The target groups are mainly MSM and transgender persons at high risk of HIV infection, as well as other subjects at risk of HIV infection due to their sexual practices.

Objectives include assessment of the following:

- Assess the impact of PrEP on the sexual and psychological health of PrEP users
- Incidence of sexually transmitted infections (STIs) in PrEP users compared to those not taking PrEP
- Assessment of drug compliance
- Incidence of HIV seroconversion despite PrEP
- Frequency and development of drug resistance in subjects who HIV-seroconvert (if any)

3 POPULATION

3.1 Inclusion Criteria

In order to participate in the PrEP arm of this study the subjects must meet all of the following inclusion criteria:

1. Male, female or transgender persons aged ≥ 18 years who are offered or have started PrEP in routine clinical practice, and 2, 3, 4, 5, 6 or 7 (below).
2. Men who have sex with men (MSM) and transgender persons;
 - a. who have had unprotected anal sex with two or more partners during the last six months and/or
 - b. who have had bacterial sexually transmittable infection(s) during the last twelve months and/or
 - c. who have used post-exposure prophylaxis(PEP) during the last twelve months and/or
 - d. who use recreational drugs when having sex
3. Indication for PrEP is present according to the assessment of the health care provider
4. Men and women who are at high risk of HIV according to their sexual practices
5. HIV-negative partner of a HIV-positive person not yet virologically suppressed by antiretroviral therapy (ART)
6. Sex workers with inconsistent condom use
7. Persons with inconsistent condom use with sexual partners in / from countries with a high prevalence of HIV (COHP)

Subjects who are included in the PrEP arm will act as their own controls regarding possible changes in psychological and sexual health. At the screening visit they will complete questionnaire requesting information related to last 6 months prior to study start. Individuals who seroconvert during the observational period will be transferred to the out-patient clinic for Infectious Diseases as is already standard of care.

Patients diagnosed with HIV in general clinical practice and referred to the out-patient clinic at the Dept. of Infectious Diseases, OUS, will be asked to act as controls to assess their past psychological and sexual health. They will be asked to sign the consent form and answer the same questionnaire as those in the PrEP arm but not followed further in this study.

Frequency of STI reported to the National Institute of Public Health (MSIS) will be compared with the frequency of STIs in the study cohort.

3.2 Exclusion Criteria

In order to participate in the study subjects must not meet any of the following exclusion criteria:

1. HIV positive subjects
2. Subjects who cannot take FTC/TDF due to contraindications

3.3 Control Group

Subject to be included in the control group:

1. Enrolled patients will be regarded as their own control when it comes to their sexual health and quality of life reported for period prior to inclusion in the study.
2. Subjects newly diagnosed with HIV in general clinical practice and referred to the out-patient clinic at the Dept. of Infectious Diseases, OUS, who meet the following inclusion and exclusion criteria:
 - a. Inclusion criteria in the control group:
 - i. Confirmed positive HIV-test, AND
 1. Confirmed negative HIV-test < 12 months ago, OR
 2. Self-reported assumed time of infection < 12 months ago, AND
 - ii. Resident for > 6 months in a country of one of the following regions (EU/EFTA, North America or Australia/New Zealand) at the time of confirmed or assumed infection.
 - b. Exclusion criteria in the control group:
 - i. Confirmed positive HIV-test > 12 months ago, OR
 - ii. Self-reported assumes time of infection > 12 months ago.
3. Frequency of STI reported to the National Institute of Public Health (MSIS) will be compared with the frequency of STIs in the study cohort.

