3.4 Recruitment and Screening

Individuals attending the clinic for PrEP assessment are either referred from other health care providers or referred by themselves (self-referral).

Those who have commenced PrEP elsewhere (abroad, purchased themselves, another provider) and attend for "PrEP follow-up" either at Olafiaklinikken or a corresponding venereological clinic/study site in Norway, may also be included in the study.

Eligible subjects will have the study explained to them, and will receive the written informed consent form (ICF). After having had the time to review the nature of the study, they will have the opportunity to ask questions to the investigating team. If the subject agrees to participate, they will be asked to sign and date one original written informed consent form (ICF). The subject will then receive a copy of the signed and dated patient information/informed consent form. The original signed ICF will be filed in the Investigator Site File (ISF). The PIS will contain site contact information in case of any questions or medical emergency.

Newly diagnosed HIV positive individuals referred to the out-patient clinic of the Dept. of Infectious Diseases, OUS, will be invited to participate as controls. The inclusion and exclusion criteria for the control group aim at including newly infected individuals (< 12 months) residing in a country for > 6 months where PrEP might have been available, and excluding individuals infected long time ago in a country where PrEP was inaccessible; i.e. mostly countries with high HIV-prevalence outside the EU/EFTA-region, North America and Australia/New Zealand. They will be presented with the same consent form and questionnaire on sexual and psychological health prior to the HIV diagnosis.

Any written information given to potential subjects will be submitted to, and approved by, the Ethics Committee(s) prior to implementation.

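### The own-control baseline is set by inclusion, not by first PrEP use, so for subjects already on PrEP the before-after change is partly or wholly PrEP against PrEP, and the supplied analysis text does not separate them from new starters

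*Protocol*

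**What the plan says.** - **Objective.** Protocol 1.1 begins: "The main objective of this study is to monitor the impact of PrEP on the", and goes on to name psychological and sexual health.
- **Who may enrol.** Inclusion criterion 1 (Protocol 3.1) covers persons "who are offered or have started PrEP in routine clinical practice". Protocol 3.4 adds: "Those who have commenced PrEP elsewhere (abroad, purchased themselves, another provider) and attend" for follow-up may also join. Protocol 4.1 repeats that current users are eligible. None of these places limits how long PrEP has been used.
- **Baseline.** Protocol 3.3, item 1, makes enrolled subjects their own control for "their sexual health and quality of life reported for period prior to inclusion in the study". Protocol 3.1 says that at screening they complete a "questionnaire requesting information related to last 6 months prior to study start". The Protocol outline describes the content as including "sexual behaviour the last 6 months, perception of HIV risk at the last condomless sex".
- **Follow-up.** Under the Protocol outline, subjects will "answer the same questions regarding sexual behaviour and quality of life at follow up visits as at inclusion study visit". Visits are about every 3 months for 24 months.
- **Extra data for current users.** Protocol 4.1 asks them to consent to collection of medical history from the date PrEP began.
- **Other controls.** People newly diagnosed with HIV "answer the same questionnaire as those in the PrEP arm but not followed further in this study" (Protocol 3.1). The national surveillance comparison concerns STI frequency only (3.3, item 3).
- **Analysis.** Sections 7.2 to 7.4 describe enrolled PrEP-treated subjects by time point, using the nearest available measurement. They make no distinction by prior PrEP use.

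The document supplied as the SAP repeats the text relied on here in its own 3.1, 3.3, 3.4, 4.1 and 7.2 to 7.4.

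**The concern.** A before-after contrast measures the impact of PrEP only if the first measurement precedes PrEP. The plan ties that measurement to inclusion and also admits people whose PrEP use began earlier. A new starter's baseline describes life without PrEP. After 6 or more months of use, the same window describes life on PrEP, and after shorter use it is a blend.

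Nothing else in the supplied text restores the missing comparison. History collected from PrEP start onward is on-PrEP time by construction. The HIV-diagnosed controls answer once and give no within-subject change.

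What is at stake is the reading of the main objective. A summary over all enrolled subjects would combine two different contrasts, in a proportion that the plan neither fixes nor reports.

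**Working it through.** The plan gives no figure to reproduce: sample size is marked not applicable, and no effect size or power is stated. The size can only be illustrated.

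**Inputs from the documents.** Recall window of 6 months before study start (Protocol 3.1); the same questions repeated at follow-up (Protocol outline); visits about every 3 months.

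**Assumed inputs, not in the documents.** p, the share of enrolled subjects already on PrEP: 10%, 30% or 50%. m, their months on PrEP at inclusion: 1, 3, or 6 and more. PrEP causes an immediate, constant shift D. Recall is 6 months at both times.

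**Step 1: individual change.** The share of the baseline window spent on PrEP is min(m, 6)/6. At t months after inclusion (for a new starter, after PrEP start) it is min(m + t, 6)/6. Hence

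change at month t = D × [min(m + t, 6) − min(m, 6)]/6.

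| Prior months m | Month 3 | Month 6 or later |
|---|---|---|
| 0 (new starter) | (3 − 0)/6 = 0.50 D | (6 − 0)/6 = 1.00 D |
| 1 | (4 − 1)/6 = 0.50 D | (6 − 1)/6 = 0.83 D |
| 3 | (6 − 3)/6 = 0.50 D | (6 − 3)/6 = 0.50 D |
| 6 or more | (6 − 6)/6 = 0 | 0 |

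**Step 2: pooled change from month 6.** (1 − p) × D + p × D × [1 − min(m, 6)/6] = D × [1 − p × min(m, 6)/6]. The proportional loss is p × min(m, 6)/6:

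| m | p = 10% | p = 30% | p = 50% |
|---|---|---|---|
| 1 | 1.7% | 5.0% | 8.3% |
| 3 | 5% | 15% | 25% |
| 6 or more | 10% | 30% | 50% |

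**Step 3: month 3 behaves differently.** New starters and users with m of 3 or less all show 0.5 D, so these users add no dilution relative to new starters. Users with m of 6 or more show 0, which makes the pooled change (1 − p) × 0.5 D: 0.45 D, 0.35 D and 0.25 D at the three values of p. Even new starters show only half of D at month 3, because half of their recall window precedes PrEP.

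**Step 4: relax the constant effect.** Suppose prior users change by c times the new-starter change. The pooled change relative to that of new starters is (1 − p) + p × c. With c = 1.5 it is 1.05, 1.15 and 1.25 at p = 10%, 30% and 50%. With c = −0.5 it is 0.85, 0.55 and 0.25. The mixture can therefore overstate as well as understate.

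**The case against.** The strongest reply is that the key instruments are unseen and no pooled estimator is written down. The questionnaire appendix is a heading only. Table 1 lists a sexual-behaviour form labelled for the start of treatment and another for follow-up, and marks both at Visit 0, so prior users may be handled differently. Section 7.1 of both documents defers detail to a separate SAP that was not available. Sections 7.2 to 7.4 promise descriptive summaries by time point, not a single before-after estimate. The recall period for quality of life is not shown, and a scale of current state would not follow the formula above.

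Much of this stands. It limits the arithmetic to an illustration, and it means that the unseen documents could already contain the separation. It does not remove the point. The baseline rule stands in Protocol 3.3 itself, and Protocol 3.1 gives its window. A form that asked prior users about the time before PrEP would depart from both sections, and Table 1 does not say who receives which form. Descriptive summaries are also still the evidence offered for the impact of PrEP.

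A reader might infer three stronger things that the documents do not support:

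- **That the change is biased toward zero.** This needs an immediate, constant effect, which is assumed and not documented.
- **That restriction to new starters recovers the full effect at every visit.** Under 6-month recall it does so only from month 6.
- **That STI history is affected in the same way.** It is taken at Visit 0 (Table 1 and Section 6) without being limited to time on PrEP.

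**Conclusion.** The point holds as a statement about the baseline. For subjects who used PrEP in the 6 months before inclusion, the stated own-control rule compares PrEP with PrEP in part or in whole, and the supplied analysis text leaves them undistinguished from new starters. That the contrast is mixed follows from the text once any such subject enrols.

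Direction and size are not known. Under an immediate, constant effect with 6-month recall, the loss from month 6 runs from 1.7% (p = 10%, m = 1) to 50% (p = 50%, m of 6 or more). Different behaviour over time on PrEP could reduce, remove or reverse it. The figures should not be carried over to quality of life without knowing its recall period. Because the point concerns the main objective and the remedy is small, it is worth settling before analysis.

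**What to change.** - **Data.** Record the date of first PrEP use and any PrEP use in the 6 months before Visit 0.
- **Before-after comparison.** In 3.3 (item 1), 7.2 and 7.3, base the comparison of behaviour and quality of life on subjects with no PrEP use in that window, summarised as within-subject change. Use only follow-up points whose recall window lies wholly after PrEP start: month 6 onward if recall is 6 months.
- **Prior users.** Report subjects with PrEP use in the window separately, with their number and prior months on PrEP. Label the result as change during PrEP, not as a before-PrEP contrast.
- **Lapsed users.** Show people whose PrEP use ended before the window as their own category. Their window is free of PrEP, but they are not new to it.
- **Forms.** State which Table 1 questionnaire each group receives and the recall period of each.

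**Cost.** A date, a use item and some wording; Protocol 4.1 already relies on the PrEP start date. The before-after comparison has fewer subjects. With equal variances its standard error grows by 1/√(1 − p): 1/√0.9 = 1.054, 1/√0.7 = 1.195 and 1/√0.5 = 1.414, that is, about 5%, 20% and 41% at p = 10%, 30% and 50%. No sample-size target is breached, since none is set. Enrolment and care do not change.

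### The crude comparison of HIV-diagnosed controls with the mainly MSM/transgender PrEP arm is confounded by risk-group mix, and no stratification or adjustment is planned

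*Protocol*

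**What the plan says.** **PrEP arm.** Protocol section 3.1 opens: "In order to participate in the PrEP arm of this study the subjects must meet all of the following inclusion criteria". The participant must be at least 18, have been offered or have started PrEP, and meet at least one of criteria 2 to 7. Section 2 describes who is expected: "The target groups are mainly MSM and transgender persons at high risk of HIV infection".

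**HIV-diagnosed controls.** Section 3.3 item 2 takes "Subjects newly diagnosed with HIV in general clinical practice and referred to the out-patient clinic at the Dept. of Infectious Diseases" at one Oslo hospital. Besides a confirmed positive test, the criteria are:

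- recency, by test ("Confirmed negative HIV-test < 12 months ago, OR") or by self-report ("Self-reported assumed time of infection < 12 months ago, AND");
- residence: "Resident for > 6 months in a country of one of the following regions", namely EU/EFTA, North America or Australia/New Zealand.

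No item concerns route of infection, MSM or transgender status, sexual risk or age. Section 3.4 explains that the aim is to find recent infections in places where PrEP could have been obtained. These controls complete, once, the same "questionnaire on sexual and psychological health prior to the HIV diagnosis".

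**Analysis.** Section 7.2 describes data on participants receiving PrEP, and section 7.3 gives summary statistics only. Neither mentions the controls, risk groups, matching or adjustment. The SAP repeats this text, and its section 3.3 lacks even the recency and residence limits.

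**The concern.** Section 3.1 enrols these controls so that their past psychological and sexual health can be assessed, which is the subject of the study's main objective. Partner numbers, condom use and drug use may well differ between MSM/transgender persons and others. If the two groups contain different shares of these populations, an unstratified table will show a difference even where PrEP users and controls of the same risk group answered identically. A reader of the study report could then attribute to PrEP use, or to the circumstances of infection, a difference that arises from who was sampled.

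**Working it through.** **The plan's own figure.** Protocol section 1 reports 220 new diagnoses in 2016, of which 70 were acquired before immigration: 220 − 70 = 150 among residents. It then says "MSM were over-represented with 87 (58%) new HIV infections": 87/150 = 58%, which reproduces. The remainder is 63/150 = 42% not recorded as MSM.

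**Inputs.**

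- MSM share of controls, m_C: not in the documents. 58% is the nearest proxy; 75% and 90% are assumed alternatives.
- MSM share of the PrEP arm, m_P: described only as the main part; assumed 90 to 100%.
- Behaviour gap, g, the difference in the frequency of a questionnaire item between MSM and others: assumed 20 to 50 percentage points.

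**Formula.** Let an item be present in a proportion a of MSM and b of others, the same in both study groups, so that there is no true difference within risk group. The crude frequency in a group with MSM share m is m·a + (1 − m)·b. Subtracting controls from the PrEP arm gives

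spurious difference = (m_P − m_C) × (a − b) = (m_P − m_C) × g.

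**Results.**

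| Controls' MSM share | Low: m_P = 90%, g = 20 points | High: m_P = 100%, g = 50 points |
|---|---|---|
| 58% | (0.90 − 0.58) × 0.20 = 0.064 | (1.00 − 0.58) × 0.50 = 0.210 |
| 75% | (0.90 − 0.75) × 0.20 = 0.030 | (1.00 − 0.75) × 0.50 = 0.125 |
| 90% | (0.90 − 0.90) × 0.20 = 0.000 | (1.00 − 0.90) × 0.50 = 0.050 |

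That is about 6 to 21, 3 to 13 and 0 to 5 percentage points.

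**After the fix.** Within a risk group, or after standardising controls to the PrEP arm's mix, m_P − m_C = 0 and this term vanishes.

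**The case against.** The strongest opposing case has four parts.

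1. **The proxy is weak.** The 58% covers every 2016 diagnosis among residents, not recent infections referred to one clinic. This stands. The controls' mix is unknown, and if they are nearly all MSM the problem almost disappears.

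2. **No formal contrast is announced.** The participants' own earlier answers serve for change over time, the national surveillance data serve for STI frequency, and the analysis is descriptive. Section 7.1 also defers detail to a separate document, and the supplied SAP only repeats that deferral. This limits how much of the study is affected, but a descriptive table of two differently composed groups has the same flaw, and nothing in either document guards against it.

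3. **The entry criteria are deliberate.** Section 3.4 gives a reason for them. A reader might infer that controls should have to meet a PrEP criterion at entry. The documents do not support that. Criteria 3 to 7 admit men and women who are not MSM, so the requirement would not equalise MSM shares. It would also prevent the study from counting recently infected people who would not have qualified.

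4. **The data to deal with this are already planned.** Controls answer the same questionnaire, which the Protocol Outline says covers demographics, sexual behaviour, STI history and drug use; section 6 lists gender and sexuality. This is correct, and it is why the remedy is cheap. The plan does not say that these data will be used in this way.

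Two further inferences go too far. One is that any observed difference would be nothing but mix: the documents show that mix cannot be separated from other causes, not that other causes are absent. The other is that 42% of controls would have been ineligible for PrEP: the figure counts people not recorded as MSM, many of whom could have met the broad criteria 3 to 7.

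**Conclusion.** The point holds as confounding. As written, a crude comparison of HIV-diagnosed controls with the PrEP arm mixes risk-group composition with everything else. With 58% MSM taken as a proxy for the controls, mix alone would contribute about 6 to 21 percentage points to a yes/no item; with 75% about 3 to 13, and with 90% about 0 to 5. All three ranges rest on an assumed 90 to 100% MSM in the PrEP arm and assumed gaps of 20 to 50 points. The documents supply only the 58%, and for a different population. The own-control and national surveillance comparisons are not affected by this point.

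**What to change.** Leave the control entry criteria in Protocol section 3.3 as they are. In sections 7.2 and 7.3, and in the SAP, state that:

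- the control comparison is reported separately for MSM/transgender participants and for others, or with controls standardised to the PrEP arm's mix, using the gender, sexuality and behaviour data already collected;
- the PrEP arm contributes its pre-PrEP baseline answers. Sections 3.4 and 4.1 admit people already taking PrEP, whose six months before study start may include time on PrEP; show them apart in this comparison;
- a sensitivity analysis keeps only controls whose answers show that they would have met a PrEP criterion before infection. Criterion 3, the provider's judgement, cannot be reconstructed from a questionnaire, so this rests on the others as far as the answers allow;
- psychological items are kept, since they are part of the controls' stated purpose, with a note that controls recall them after learning their diagnosis.

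Also align SAP section 3.3 with the protocol's control criteria.

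No new data collection is proposed. The cost is small strata, particularly among participants who are neither MSM nor transgender, and wider uncertainty in each. Standardisation will be unstable if a stratum is nearly empty, so the stratum counts should be shown.
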